12.9.2. Adverse Events of Special Interest

An AESI (serious or non-serious) is one of scientific and medical concern, for which ongoing monitoring and rapid communication by the Investigator to the sponsor could be appropriate. AESIs must be reported within 24 hours of occurrence or when the Investigator becomes aware of the event, following SAE reporting procedures (Section 12.9.4). Such an event might require

further investigation in order to characterize and understand it. Depending on the nature of the event, rapid communication by the trial sponsor to other parties (eg, regulators) might also be warranted.

In this trial, the following AEs are to be considered AESIs:

- Any AE of occurrence of suicidal ideation or behavior, including a positive response to question 1 to 5 of C-SSRS
- A depression assessed as moderate or worse by the Investigator or a score ≥15 in the HADS score
- Any grade 3 or higher psychiatric condition
- Any weight loss >5% compared to Baseline, and/or
- Any of the following GI TEAEs: vomiting, diarrhea with an increase of at least four stools per day over Baseline (Grade 2 CTCAE) for at least 3 days.

12.9.3. Serious Adverse Events

[figure not shown]
An SAE is any untoward medical occurrence, in the view of either the Investigator or Sponsor, that:

- results in death.
- is life threatening,
- results in inpatient hospitalization or prolongation of existing hospitalization,
- results in persistent or significant disability/incapacity, and/or
- is a congenital anomaly/birth defect
- results from overdose

Other important medical events that may not be immediately life threatening or result in death or hospitalization, based upon appropriate medical judgment, are considered SAEs if they are thought to jeopardize the patient and/or require medical or surgical intervention to prevent one of the outcomes defining an SAE. SAEs are critically important for the identification of significant safety problems; therefore, it is important to take into account both the Investigator's and the Sponsor's assessment. If either the Sponsor or the Investigator believes that an event is serious, the event must be considered serious and evaluated by the Sponsor for expedited reporting.

12.9.4. Serious Adverse Event Reporting

An SAE occurring from the time informed consent is obtained, during the study, or within 30 days of stopping the treatment must be reported to Health Safety and Pharmacovigilance group and will be communicated to the Sponsor. Any such SAE due to any cause, whether or not related to the study drug, must be reported immediately, and under no circumstances later than

Safety and Pharmacovigilance

• Safety and Pharmacovigilance email address:

If the Investigator contacts the Safety and Pharmacovigilance group by telephone, then a written report must follow within 24 hours and is to include a full description of the event and sequelae in the format detailed in the SAE reporting form.

The event must also be recorded on the standard AE eCRF. Preliminary reports of SAEs must be followed up by detailed descriptions later on, including clear and anonymized photocopies of hospital case reports, consultant reports, autopsy reports, and other documents when requested and applicable. SAE reports must be made whether or not the Investigator considers the event to be related to the investigational drug.

Appropriate remedial measures should be taken to treat the SAE, and the response should be recorded. Clinical, laboratory, and diagnostic measures should be employed as needed to determine the etiology of the problem. The Investigator must report all additional Follow-up evaluations to Safety and Pharmacovigilance group within 24 hours of becoming aware of the additional information or as soon as is practicable. All SAEs will be followed up until the Investigator and Sponsor agree the event is satisfactorily resolved.

Any SAE that is not resolved by the end of the study or upon discontinuation of the patient's participation in the study is to be followed up until it either resolves, stabilizes, returns to Baseline values (if a Baseline value is available), or is shown to not be attributable to the study drug or procedures.

12.9.5. Suspected Unexpected Serious Adverse Reactions

AEs that meet all of the following criteria will be classified as suspected unexpected serious adverse reactions (SUSARs) and reported to the appropriate regulatory authorities in accordance with applicable regulatory requirements for expedited reporting:

- serious
- unexpected (ie, the event is not consistent with the safety information in the Investigator's Brochure)
- there is at least a reasonable possibility that there is a causal relationship between the event and the study treatment

The Investigator will assess whether or not an event is causally related to study treatment.

will consider the Investigator's assessment and determine whether or not the event meets the criteria for being reportable as a 7-day or 15-day safety report. SUSARs that are fatal, or life threatening must be reported to the regulatory authorities and the IEC/IRB (where

required) within 7 days after the ____/UNION therapeutics A/S has first knowledge of them, with a Follow-up report (when applicable) submitted within a further 8 calendar days. Other SUSARs must be reported to the relevant regulatory authorities and the IEC/IRBs within 15 calendar days after the ____/UNION therapeutics A/S first has knowledge of them.

The Sponsor is responsible for reporting SUSARs, and any other events required to be reported in an expedited manner to the regulatory authorities and for informing investigators of reportable events, in compliance with applicable regulatory requirements within specific timeframes. Investigators will notify the relevant IRB/IEC of reportable events within the applicable timeframes.

12.9.6. Pregnancy

WOCBP must have a negative serum pregnancy test at Screening and are required to use one of the highly effective contraception methods (Inclusion Criterion 7). Women on hormone replacement therapy, and whose menopausal status is in doubt, will be required to use one of the highly effective contraception methods. Highly effective contraception is defined as having a failure rate of less than 1% per year when used consistently and correctly and, when applicable, in accordance with the product label.

Women of nonreproductive potential are defined as those with surgical sterilization (hysterectomy, bilateral oophorectomy, or bilateral salpingectomy) and those in a postmenopausal status defined as cessation of menses for at least 12 months without an alternative medical cause, and a confirmatory FSH test or as cessation of menses for at least 24 months without an alternative medical cause.

After administration of study drug, any known cases of pregnancy in female patients will be reported until the patient completes or withdraws from the study. The pregnancy will be reported immediately by faxing/emailing a completed pregnancy report to Safety and Pharmacovigilance within 24 hours of knowledge of the event. If any patient becomes pregnant during the study, they are to immediately discontinue any UNION-supplied study drug and to have only safety assessments performed. The Investigator will Follow up with the patient until completion of the pregnancy and must assess the outcome in the shortest possible time but not more than 30 days after completion of the pregnancy. The Investigator should notify and Pharmacovigilance of the pregnancy outcome by submitting a Follow-up pregnancy report. If the outcome of the pregnancy involved spontaneous or therapeutic abortion (any congenital anomaly detected in an aborted fetus is to be documented), stillbirth, neonatal death, or congenital anomaly, the Investigator will report the event by faxing/emailing a completed pregnancy report form to and Pharmacovigilance within 24 hours of knowledge of the event. If the Investigator becomes aware of a pregnancy occurring in the partner of a patient participating in the study, the pregnancy should be reported to Pharmacovigilance within 24 hours of knowledge of the event. Information regarding the pregnancy must only be submitted after obtaining written consent from the pregnant partner. The Investigator will arrange counseling for the pregnant partner by a specialist to discuss the risks of continuing with the pregnancy and the possible effects on the fetus.

Upon discontinuation from the study, only those procedures that would not expose the patient to undue risk will be performed. The Investigator should also be notified of pregnancy occurring during the study but confirmed after completion of the study. If a patient is subsequently found to be pregnant after inclusion in the study, any pregnancy will be followed to term, and the status of mother and child will be reported to and Pharmacovigilance after delivery.

12.9.7. Overdose

In case of suspected overdose, please contact the Sponsor immediately.

13. PHARMACOKINETICS

13.1. Pharmacokinetic Sampling

[figure not shown]
13.1.1. Blood Samples

Blood samples of approximately mL will be collected for measurement of concentrations of orismilast and its major metabolite (LEO 40815) as specified in the Schedule of Assessments (Table 4) before dose of the study drug. The actual date and time of each blood sample collection will be recorded.

Blood sampling for measuring trough levels: The blood collection for PK analysis should preferably be conducted approximately hours after the last study drug administration. It is recommended to have date and time of patient's last drug intake before PK sampling recorded in patient's source and in the eCRF as well.

Blood sampling for calculation of PK profiles: In addition to the sample collected for measuring trough levels, patients will be offered optional participation in specific blood sampling for calculation of PK profiles. This additional procedure is voluntary for patients and patient's consent will be obtained before collection of the blood samples. For PK profiling, additional blood samples will be collected during each visit at and and and are the patient will be instructed to take the next dose of the study drug in the clinic and blood samples will be taken at the following timepoints: (estimated C_{max}), after intake of the study drug, as shown in Figure 2. An additional optional blood sample will be collected if possible for the patient. The actual date and time of the study drug administration in the clinic and each blood sample collection will be recorded.

Figure 2 Pharmacokinetic Blood Sample Collection

Abbreviations: Lab, laboratory; PK, pharmacokinetics

Details of PK blood sample collection, processing, storage, and shipping procedures are provided in a separate laboratory manual.

UNION therapeutics A/S
Orismilast
UNI50001-203
Version 3.0

13.2. Pharmacokinetic Analytical Methodology

The concentration of study drug will be determined from the plasma samples using a validated analytical method. Details of the method validation and sample analysis will be included with the final clinical study report.

14. PHARMACODYNAMICS

15. STATISTICAL ANALYSIS

A statistical analysis plan will be prepared after the protocol is approved. This document will provide further details regarding the definition of analysis variables and analysis methodology to address all study objectives. The statistical analysis plan will serve as a compliment to the protocol and supersedes it in case of differences.

The statistical evaluation will be performed using SAS® software version 9.4 or higher (SAS Institute, Cary, NC). All data will be listed, and summary tables will be provided. Summary statistics will be presented by treatment group. For continuous variables, data will be summarized with the number of patients (N), mean, standard deviation, median, minimum, and maximum by treatment group. For categorical variables, data will be tabulated with the number and proportion of patients for each category by treatment group.

15.1. Determination of Sample Size

Approximately 200 patients will be enrolled to ensure approximately 50 patients per arm. This sample size is based on assumptions that the percentage change from Baseline in PASI is -32.2% and -50.9% for placebo and each orismilast dose group, respectively, and the standard deviation is 33%. Using a 2-sided 2-sample *t*-test, 50 patients in each treatment arm can achieve a power of 80% at the significance level of 5%.

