5.2.2.2. Efficacy

So far one efficacy trial (LP0058-1072) with orismilast immediate-release tablets has been completed. A total of 36 subjects with moderate-to-severe psoriasis vulgaris were randomized in the trial in a 1:1 ratio to treatment with either 30 mg orismilast or placebo, administered orally as 3 tablets twice daily for 16 weeks (1-week dose escalation followed by 15-week full dose treatment).

After 16 weeks of treatment, the mean psoriasis area and severity index (PASI) score (primary endpoint) was statistically significantly lower in subjects treated with orismilast tablets (least squares mean: 7.1) compared with subjects in the placebo group (least squares mean: 13.1). Mean PASI at entry was 14.9. A higher proportion of patients achieved a 75% improvement in PASI (PASI75) in the orismilast group (44.4%) vs placebo (5.6%; P =.019). In addition, treatment success (defined as clear or almost clear) according to Physician's Global Assessment of disease severity (PGA) at Week 16 was higher in the orismilast group (7 of 18 subjects, 38.9%) than in the placebo group (1 of 18 subjects, 5.6%). The estimated itch score was numerically lower at Week 16 in the orismilast group (least squares mean: 3.4) compared with the placebo group (least squares mean: 5.7).

Approximately half of the subjects in both treatment groups were withdrawn from the LP0058-1072 trial, mainly owing to tolerability issues in the orismilast group and lack of efficacy in the placebo group, respectively. Although the bias introduced by this attrition had an impact on the estimated efficacy, it was not considered to disqualify the clear difference observed between the 2 treatments.

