9.2. Measures to Minimize Bias: Study Treatments

9.2.1. Method of Study Treatment Assignment

At the investigational site, each screened patient will be assigned a patient identifier number during Screening that will be used on all patient documentation. The patient identifier number will contain the site number and the patient number and will be assigned in numerical order at the Screening visit based on chronological order of Screening dates (eg, 01-010 for the 10th patient screened at the Site #01).

Randomization will occur prior to first study treatment administration, at the Baseline visit. Patients will be assigned randomly in a 1:1:1:1 ratio to 1 of 3 orismilast dose groups (20 mg, 30 mg, or 40 mg) or placebo.

A randomization list will be used to assign the treatments to each patient. The randomization list will be kept secured with access restricted to only the designated personnel directly responsible for labeling and handling the study drug until the study blind is broken at the end of study (database lock). Further guidance and information can be obtained in the study manual.

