15.3.1. Analysis of Primary Efficacy Endpoint

The primary endpoint, percentage change from Baseline to Week 16 in PASI, will be analyzed using analysis of covariance with treatment group as factor and Baseline PASI as covariate. As a supportive analysis, a mixed model for repeated measure (MMRM) will be performed with treatment group, visit and treatment-by-visit interaction as factors and Baseline PASI score by-visit interaction as a covariates.

Each active treatment dose will be compared with placebo. No adjustment for multiplicity will be made and the 0.05 level of significance will be used to claim efficacy compared with placebo. Least square means and the 95% confidence interval of the difference between each active treatment and placebo will be calculated. The primary analysis set will be the ITT Analysis Population with multiple imputation approach to handle missing values. The same analyses will be repeated for Weeks 20, 12, 8 and 4.

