#### **4.3. Determination of Sample Size**

Approximately 200 patients will be enrolled to ensure approximately 50 patients per arm. This sample size is based on assumptions that the percentage change from Baseline in PASI is -32.2% and -50.9% for placebo and each orismilast dose group, respectively, and the standard deviation is 33% (1, 2). Using a 2-sided 2-sample t-test, 50 patients in each treatment arm can achieve a power of 80% at the significance level of 5%.

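### The stated 80% power assumes that all 50 enrolled patients per arm have a Week 16 PASI; it carries no allowance for missing values and should be restated at an assumed missing rate

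*Protocol*

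**What the plan says.** The sample size statement is the same in the synopsis, Protocol 15.1 and SAP 4.3. The assumed "percentage change from Baseline in PASI is -32.2% and -50.9% for placebo and each orismilast dose group, respectively", and "the standard deviation is 33" percent. Protocol 15.1 then concludes, for a two-sided two-sample t-test, that "50 patients in each treatment arm can achieve a power of 80% at the significance level of 5" percent. On enrolment SAP 4.3 says: "Approximately 200 patients will be enrolled to ensure approximately 50 patients per arm". None of the three places gives a dropout rate, a number of evaluable patients or an inflation step. Protocol 8.4 has replacement of patients in its heading but no replacement rule in its text.

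Allocation is equal across four arms (Protocol 9.2.1), and each dose is tested against placebo on its own: "No adjustment for multiplicity will be made and the 0.05 level of significance will be used to claim efficacy" (Protocol 15.3.1).

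Other sections provide for missing Week 16 data:

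- SAP 9 sets out multiple imputation for values missing after early discontinuation, assuming missing at random within arm (also SAP 7.3).
- SAP 8.1 plans a Kaplan-Meier plot of time to treatment discontinuation.
- Protocol 9.3 keeps patients who permanently stop drug in the study for safety evaluation; it does not mention continued efficacy visits.
- SAP 7.4 counts a discontinued patient's end-of-treatment PASI as Week 16 only if it falls between Day 99 and Day 139.
- Protocol 5.2.2.2 reports on the sponsor's Phase 2a trial: "Approximately half of the subjects in both treatment groups were withdrawn from the LP0058-1072 trial".

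**The concern.** The calculation treats the number enrolled as the number with a Week 16 PASI. That would matter little if 50 per arm included some slack, but it is the exact minimum for 80% under the stated test. Any material amount of missing Week 16 data therefore takes the comparison below the quoted power on the plan's own terms.

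At stake is how a non-significant dose is read. The study is meant to choose a dose for Phase 3 (Protocol 6.1.2), and each of the three doses has its own test at 0.05. A reader told that power is 80% will give a negative comparison more weight than one told that it is, say, 75%. Protocol 5.2.2.3 reports that adverse events increased with dose, so losses need not be equal across arms.

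**Working it through.** **Inputs from the documents.** Difference Δ = 50.9 − 32.2 = 18.7 percentage points; SD σ = 33; two-sided α = 0.05; n = 50 per arm; equal allocation; two-sample t-test.

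**Step 1: reproduce the stated figure.** The noncentrality is δ = Δ / (σ√(2/n)), and power is the probability that a noncentral t variable with 2n − 2 degrees of freedom exceeds the critical value in absolute size.

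- n = 50: δ = 18.7 / (33 × √0.04) = 18.7 / 6.6 = 2.833; df = 98; critical value 1.984; power **80.1%**. The plan's figure is reproduced.
- n = 49: δ = 2.805; df = 96; critical value 1.985; power **79.3%**.

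So 50 is the smallest n that reaches 80%. The normal approximation is slightly more generous (80.9% at 50, and 49 suffice), which does not change the picture.

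**Step 2: small losses.** One value missing in one arm gives 79.7%, which still rounds to 80%. With equal losses in both arms, 48 per arm gives 78.5% and 47 gives 77.6%. The shortfall from 80% passes 2 points at three missing per arm (6%).

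**Step 3: larger losses.** The documents give no planning rate, so the missing proportions m below are assumptions, taken as equal in both arms.

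- *Lower bound:* patients without a Week 16 PASI add nothing, so n = 50(1 − m).
- *Partial recovery:* imputation borrows from PASI at Weeks 4, 8 and 12. A rough effective size is n = 50[1 − m(1 − ρ²)], where ρ is the correlation of Week 16 with the earlier visits. The documents give no ρ; 0.5 to 0.9 is assumed.

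| Missing Week 16 PASI | n, no recovery | Power, no recovery | Effective n, ρ = 0.5 to 0.9 | Power, partial recovery |
|---|---|---|---|---|
| 10% | 45 | 75.8% | 46.3 to 49.1 | 76.9% to 79.3% |
| 15% | 42.5 | 73.3% | 44.4 to 48.6 | 75.2% to 78.9% |
| 20% | 40 | 70.6% | 42.5 to 48.1 | 73.3% to 78.5% |
| 30% | 35 | 64.7% | 38.8 to 47.2 | 69.2% to 77.7% |

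Example at 20% and ρ = 0.5: 50 × [1 − 0.2 × 0.75] = 42.5, power 73.3%.

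**Step 4: possible offset from ANCOVA.** If baseline PASI has correlation r with percentage change, the residual SD is 33√(1 − r²). With r = 0.3 it is 33 × √0.91 = 31.5. Power at 10% missing with no recovery is then 79.6%, so r of about 0.3 is needed to cancel a 10% loss; about 0.45 is needed for 20% (80.0%). Combining r = 0.3 with ρ = 0.7 gives about 81% at 15% missing and 77% at 30%. Both correlations are assumptions.

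**The case against.** The case on the other side is substantial, and much of it stands.

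- *The arithmetic is right.* It is. The gap is an unstated assumption, not a miscalculation.
- *Stopping drug is not the same as losing the endpoint.* Correct. Early discontinuers are asked back for end-of-treatment assessments (Protocol 8.4), a visit on Day 99 to 139 counts as Week 16, and unscheduled assessments may fill a gap (SAP 7.4). A reader might infer that any discontinuation breaks the 80%; the documents do not support that. The loss comes from a missing Week 16 PASI, and one or two per arm are trivial.
- *Multiple imputation keeps every treated patient in the analysis.* It keeps the headcount and some of the information, so the no-recovery column is a bound, not a forecast. It does not restore everything: at every assumed ρ in the table, power stays below 80%.
- *ANCOVA may recover the rest.* Possibly, as Step 4 shows. A reader might infer that the design misses 80% at every realistic discontinuation rate; that is not established. Equally, the documents state no correlation and claim no precision gain, so the offset cannot be relied on.
- *Phase 2a is a poor guide.* It had 36 patients on the immediate-release tablet, and Protocol 5.3 expects the modified-release tablet to be better tolerated. Half withdrawn is an upper scenario only.
- *Discontinued active patients might be treated as drifting to placebo-like scores, which would shrink the effect as well as the sample.* That is not the planned analysis, which imputes within arm under missing at random. The planning means cite published trials (SAP 4.3) and may already reflect dropouts, so diluting them again could count the loss twice.
- *The consequence is limited.* The p-values are nominal (SAP 7.1), and confidence intervals are reported for each dose difference. That lowers the stakes but does not make the stated power complete.

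**Conclusion.** The point holds in a limited form. The 80% is the t-test power with a Week 16 PASI from every enrolled patient, and it has no margin: 80.1% at 50 per arm, 79.3% at 49, and more than 2 points short once about three per arm are missing. The size of any larger shortfall depends on an assumed missing rate, on how well earlier visits predict Week 16, and on the baseline correlation, none of which the documents give. At 15% missing, the t-test basis gives 73.3% as the lower bound and about 75–79% with partial recovery; at 30%, 64.7% and about 69–78%. Baseline adjustment could raise these figures. The lower bound covers lost information only and takes the planned difference and SD as given. The documents do not show that the trial is badly underpowered. They show that the quoted power rests on complete Week 16 data, which the plan itself does not expect.

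**What to change.** Keep 200 patients and leave the analysis unchanged. In Protocol 15.1, the synopsis and SAP 4.3:

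1. Say that 80% power requires 50 patients per arm with a Week 16 PASI.
2. State the proportion assumed to lack one, with its basis.
3. Restate power at that proportion under the planned ANCOVA with multiple imputation, naming the visit and baseline correlations used, and give the completer t-test value beside it as the lower bound (for example 73.3% at 15% missing).

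The cost is wording and a short calculation. The downside is that the stated power may look slightly less favourable.
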